4.2.3.3 Primary Analysis of Secondary Endpoints for RTP

Descriptive statistics will be presented for S-K levels for all timepoints for each S-K was scheduled to be measured, as well as OLP baseline. The statistics will include the mean change (absolute and percent change) from baseline. In addition, a plot of S-K values by timepoint will be presented.

Similarly, the proportion of subjects who remain normokalemic will be presented by study visit.

Proportion of subjects normokalemic at Study Day 29

For the Day 29, the likelihood of being normokalemic will be compared using a logistic regression model containing the same baseline covariates as for the primary efficacy endpoint with the exception of visit and the visit-by-treatment interaction (see Section 4.2.1.4). The estimated odds ratios corresponding to the difference between the treatment arms, 95% 2-sided CI and p-values will be provided.

Proportion of subjects normokalemic during the RTP

The likelihood of being normokalemic during RTP will be analyzed using a generalized mixed model (SAS PROC GLIMMIX), which includes a random intercept and logit link. The model will include all S-K data values collected at the scheduled visits between Days 8-29, dichotomized as normal and abnormal, as response variables, and the same covariates as the model used for the main analysis of the primary endpoint (See Section 4.2.1.4).Similarly, to the approach used for the primary analysis, the model will attempt to incorporate different (unstructured) degree of dependence between the repeated observations and, if issues with model fit are observed, switch to simplified dependence structures (see Section 3.3.6). The estimated odds ratios corresponding to the difference between the treatment arms, 95% 2-sided CI and p-values will be provided.

Number of days subjects remain normokalemic

The number of normokalemic days during the RTP, inclusive of Days 8-29, will be calculated assuming that the time interval between assessments is normokalemic only if both the beginning and end assessments for that time interval display normal S-K values.

The number of normokalemic days will be analyzed using a linear regression model with the same baseline covariates as for the primary efficacy endpoint, with the exception of visit and the visit-by-treatment interaction (see Section 4.2.1.4). The results will be presented per treatment arm. The p-value (two-sided) will be provided to compare the LSMEAN of the normokalemic days between each active treatment versus placebo.

Time to hyperkalemia

The time to hyperkalemia (days) will be summarized using Kaplan-Meier life table curves and associated 95% CI points will be provided at Days 2, 5, 8, 12, 15, 19, 22 and 29 during the RTP. Kaplan-Meier curves of the time to hyperkalemia (days) will be displayed for each treatment group.

A Cox proportional hazards model (SAS PROC PHREG) will be used with the same baseline covariates as for the primary efficacy endpoint analysis, with the exception of visit and the visit-by-treatment interaction (see Section 4.2.1.4). The hazard ratio between each active treatment versus placebo will be reported along with a 95% confidence interval and a p-value.

Mean changes in S-Aldo and P-Renin levels

Descriptive statistics will be presented for nominal values, change and percent change from baseline in S-Aldo and P-Renin levels during the RTP at Randomization (Day 1), Day 15, Day 29, and EOS for each.

This endpoint will also be analyzed using a longitudinal mixed model (SAS PROC MIXED) respectively for S-Aldo and P-Renin levels. The model will include all S-Aldo and P-Renin data values collected at the scheduled visits on Days 15 and 29 as response variables, and RTP baseline values for S-Aldo and P-Renin (respectively), baseline OLP eGFR, age (<55, 55-64, >64 years) and baseline binary indicators for RAAS inhibitors, chronic kidney disease, heart failure and diabetes mellitus as covariates.

The p-value from LSMEAN (two-sided) will be provided to compare the overall mean difference in S-Aldo and P-Renin values between each active treatment (ZS 10g and ZS 5g) and placebo. The estimated mean difference in S-Aldo and P-Renin values between each of the active treatment groups (ZS 10g and ZS 5 g) relative to the placebo treatment group will be provided along with accompanying 95% confidence intervals.

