- 18. The defined wider visit window can be applied, if patients are not able to strictly follow the pre-specified visit schedules, due to a prolonged public holiday.

Study Visit	Rand. Visit	Visit 6	Visit 7	Visit 8	Visit 9	Visit 10	Visit 11	Visit 12	Visit 13	Visit 14	EOS 9
28-day randomized treatment study phase Day ⁷	Day 1 ¹²	Day 2 ¹²	Day 5 ¹²	Day 8 ¹²	Day 12 ¹²	Day 15 ¹²	Day 19 ¹²	Day 22 ¹²	Day 26 ¹²	Day 29 ¹²	Day 35 ¹²
Accepted visit window during prolonged public holidays ⁸			Day 3-6	Day 7-9	Day 10-13	Day 14-17	Day 18-20	Day 21-24	Day 25-27	Day 28-31	Day 32-43
Eligibility criteria	Х										
Physical exam including weight ^{3, 13}	Х					Х				Х	Х
Access IVRS/IWRS ¹⁰	Х			Х		Х		Х			
Study drug (IP) dispensation ¹¹	Х			Х		Х		Х			
Study drug (IP) administration ⁴	Х	Х	Х	Х	Х	Х	Х	Х	Х		
ECG ³	Х			Х		Х		Х		Х	Х
Vital signs ³	Х					Х				Х	Х
Concomitant medications	Х	Х	Х	Х	Х	Х	Х	Х	Х	Х	Х
Adverse events (including SAEs)	Х	Х	Х	Х	Х	Х	Х	Х	Х	Х	Х
Potassium ⁶	X^2	Х	Х	Х	Х	X^2	Х	Х	Х	X^2	X^2
Clinical chemistry ^{1,3}	Х					Х				Х	Х
Hematology ^{1,3}	Х					Х				Х	Х
Urinalysis 1,3	Х					Х				Х	Х
Urine HCG											X^5
IP Reconciliation										Х	

Table 2Study Plan detailing the procedures: 28-day randomized treatment study phase

1. Parameters to be measured are detailed in Table 3.

2. Potassium will be measured fasting prior to the 1st daily dose as part of the clinical chemistry panel on Day 1, 15, 29, 35 in the 28-day randomized treatment study phase.

3. Physical Exam, ECG, Vital signs, weight, urinalysis, clinical chemistry including S-Aldo and P-Renin, and hematology parameters will be measured fasting (nothing by mouth except water for a minimum of 8 hours prior to potassium sample collection at the clinic); On the 28-day randomized treatment study phase Days 1,15, 29, and 35(EOS), blood sample which including S-Aldo and P-Renin test need to be collected prior to 10am after the patient has been upright for at least 2 hours and before the ECG.

4. Study drug will be administrated in the clinic on Day 1,2,5,8,12,15,19,22 and 26. If a patient develops i-STAT potassium values between 3.0 mmol/L and 3.4 mmol/L, inclusive (confirmed by taking a second potassium

measurement after a 10 ± 2 -minute interval, and both i-STAT values meet the study drug adjustment rule), dosing will be reduced from qd to every other day for the remainder of the study.

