- 5. For women of Childbearing potential, using-HCG will be measured at clinic, using the tube provided by Central Laboratory.
- 6. All potassium samples are analyzed by i-STAT and by the Central Laboratory on all occasion. And haemolysed samples should not be sent to the Central Lab for potassium, the sample should be re-drawn to obtain a sample showing no haemolysis. For diabetic patients all blood potassium samples should be collected prior to insulin administration whenever possible.
- 7. If a scheduled clinic visit falls on a weekend or short public holiday during the 28-day randomized treatment study phase, the scheduled visit may take place either 1 day early or 1 day late (i.e., within±24 hours of the scheduled day) for the 28-day randomized treatment study phase Days 5, 8, 12, 15, 19, 22, 26 and 35, up to 2 days late for the 28-day randomized treatment study phase Day 2 or 2 days early for Day 29. If the Day 29 visit is conducted early, the patient must take IP through Day 28 per protocol.
- 8. The defined wider visit window can be applied, if patients, are not able to strictly follow the pre-specified visit schedules, due to a prolonged public holiday. If the wider visit windows are applied for a particular visit, it is important that visits before and after such a visit also follows the wider visit windows. This will only apply during prolonged public holidays. Patients are expected to follow the pre-specified visit schedule once the prolonged holiday period is over.
- 9. EOS occurs 7 ± 1 day after the last administration of IP.
- 10. Access IVRS/IWRS on visit indicated or if patient permanently discontinues dosing before the end of the 28day randomized treatment study phase.
- 11. Due to a public holiday, patients may visit the clinic up to two days after the pre-specified visit schedules, the site investigator can access the IVRS/IWRS in an earlier visit; and the system will assign the patient a new 28-day randomized treatment study phase IP kit containing an additional 7-day supply of IP.
- 12. Study Day in Table 2 is for the 28-day randomized treatment study phase.
- 13. Targeted physical examination will be conducted on Days 1, 15, 29, and Day 35 (EOS) during the 28-day randomized treatment study phase, please refer to Section 5.2.2.

4.1 **Optional Pre-screening period (Visit 1)**

The Pre-screening visit is optional. Study procedures will be performed according to the Study Plan in Table 1.

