3.3 General Considerations

All efficacy analyses will be performed separately for the open-label initial phase and the 28day randomized treatment study phase using their respective full analysis sets. Safety data will be separately summarized in a descriptive manner on the safety analysis sets for the OLP and the RTP, respectively.

All efficacy data will be listed by subject and will include S-K assessments data and efficacy response (achieve normokalemia) data. Study population listings will include disposition, protocol deviations, subjects excluded from efficacy analysis, demographic and baseline characteristics, and safety listings will include treatment compliance, adverse events, individual laboratory measurements, vital signs, physical examinations, and electrocardiograms (ECG).

Unless otherwise stated, percentages will be calculated out of the population total and for each treatment group and will be rounded to 1 decimal place. For continuous data, the mean and median will be rounded to one additional place compared to the original data, the standard deviation (SD) and standard error (SE) will be rounded to 2 additional places, and the minimum and maximum will be displayed to the same accuracy as the original data. If the number of decimal places of the original data is > 3, then the minimum and maximum will be assigned 3 decimal places, the mean and median 4 decimal places, and the SD and SE 5 decimal places.

Results of all statistical analyses will be presented using a 95% confidence interval (CI) and two-sided p-value, unless otherwise stated. All p-values will be presented to 3 decimal places. All p-values less than 0.001 will be presented as '< 0.001' and p-values greater than 0.999 will be presented as '> 0.999'.

SAS® version 9.4 or higher will be used for all analyses.

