4.2.3.2 Derivations

See section 3.3.1.1 for definition of baseline for the efficacy endpoints.

The number of days subjects remain normokalemic is calculated as the sum of the length of each period of normokalemia a subject has. The length of a period of normokalemia is calculated as the stop date of normokalemia – start date of normokalemia + 1. For subjects who have a period of normokalemia lasting for a single visit, the duration of this period is set to 1. For subjects who have a time point missing in between two visits where the subject was recorded as being normokalemic, it can be assumed that the subject remained normokalemic and extend the period of normokalemic during the RTP, the number of days subjects remain normokalemic is set to 0.Time to hyperkalemia is defined as the number of days from randomization to the date of hyperkalemia = (date of hyperkalemia -date of randomization) +1.

For analysis of time to hyperkalemia, subjects who discontinue treatment in RTP due to high S-K levels (i-STAT potassium levels > 6.2 mmol/l at the 90-minute post dose 2 blood draw) will be treated the same as the subjects who developed hyperkalemia (event). Subjects who do not become hyperkalemic during RTP will be censored at the time of the last S-K measure available for the RTP.

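### Time to hyperkalaemia (confirmatory tests 8 and 9): no ties method is named for heavily tied event times, and the software default would modestly pull the hazard ratio towards 1

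*SAP*

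**What the plan says.** SAP 4.2.3.3 gives the model for time to hyperkalaemia: "A Cox proportional hazards model (SAS PROC PHREG) will be used with the same baseline covariates as for the primary efficacy endpoint analysis". Visit and the visit-by-treatment interaction are left out. SAP 3.3 fixes the software: SAS "version 9.4 or higher will be used for all analyses". Neither document names a ties method, or an interval-censored or discrete-time alternative.

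The time scale is in SAP 4.2.3.2: "date of hyperkalemia -date of randomization) +1". This uses calendar dates and gives whole days.

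Protocol Table 2 schedules potassium after randomisation on Days 2, 5, 8, 12, 15, 19, 22, 26 and 29, which is nine visits, and again at the end-of-study visit. SAP 4.2.3.3 asks for Kaplan-Meier estimates at "Days 2, 5, 8, 12, 15, 19, 22 and 29 during the RTP". That is a reporting grid of eight days (it omits Day 26), not the event-time scale.

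Visits may move. Under the footnotes to protocol Table 2, for a weekend or short holiday, "the scheduled visit may take place either 1 day early or 1 day late"; Day 2 may be up to two days late and Day 29 up to two days early. Prolonged public holidays allow wider windows.

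The endpoint is test 8 (10 g) and test 9 (5 g), the last two in the fixed sequence of SAP Table 3 and protocol Table 6.

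**The concern.** Hyperkalaemia is found only when blood is drawn. With 250 patients and nine scheduled draws, many first events will carry the same day number. The Cox partial likelihood then needs a rule for ties. The Breslow approximation keeps every tied patient in the risk set for each tied event, and with heavy ties this pulls the estimate towards no effect. Efron largely removes that bias.

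At stake are the reported hazard ratios and confidence intervals for two confirmatory comparisons, and a little power. By the SAP's own standard this is a gap. For the mixed model it fixes REML, the covariance fallback and the degrees-of-freedom method, and for multiple imputation it fixes the seed and burn-in. The ties rule, which also changes a confirmatory p-value, is left to a default.

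**Working it through.** **1. The plan's own figure.** The documents give no power, event count or hazard ratio for this endpoint. The only power statement for the randomised comparisons is for the primary endpoint (protocol 8.2: 100 v 50 patients, difference 0.30, SD 0.50, two-sided 5%, above 90%). It reproduces:

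- SE = 0.50 × √(1/100 + 1/50) = 0.0866
- 0.30 / 0.0866 = 3.464
- Power = Φ(3.464 − 1.960) = 93.4% (93.1% with the noncentral t, 148 df)

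**2. How many event days?** Take weekday randomisation and apply the short-holiday rule: Saturday visits move to Friday, Sunday visits to Monday, and Day 2 moves late only. The possible days are 2, 4, 5, 6, 8, 11, 12, 13, 15, 18, 19, 20, 22, 25, 26, 27 and 29. That is 17 days, not nine. Moving visits at random within the window gives about 20-24 days. Ties stay heavy: across the runs below, the busiest day held on average 10 to 81 events.

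**3. Breslow against Efron on the same data.** Simulation, 350 trials per row:

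- 50 placebo, 100 on 5 g, 100 on 10 g (protocol 8.2).
- Weibull proportional-hazards onset, detected at the next visit, Day 29 cut-off.
- Cox model with treatment terms only.
- Assumed, because the documents give no values: placebo event proportion by Day 29 (40-90%), hazard ratios (0.5-0.6 for 5 g, 0.3-0.4 for 10 g) and Weibull shape (1 is constant hazard; below 1 is early clustering).

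Hazard ratios are Breslow / Efron. Shrinkage of the log hazard ratio is 1 − ln(HR Breslow) / ln(HR Efron). For example, 1 − ln(0.413)/ln(0.392) = 1 − 0.884/0.936 = 5.6%.

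| Visits | Placebo events | Shape | 5 g HR | Shrinkage | 10 g HR | Shrinkage |
|---|---|---|---|---|---|---|
| Nominal | 40% | 1 | 0.584 / 0.577 | 2.2% | 0.397 / 0.390 | 1.9% |
| Nominal | 60% | 1 | 0.618 / 0.606 | 3.9% | 0.418 / 0.406 | 3.2% |
| Nominal | 80% | 1 | 0.615 / 0.594 | 6.7% | 0.413 / 0.392 | 5.6% |
| Nominal | 80% | 0.6 | 0.532 / 0.504 | 7.9% | 0.323 / 0.299 | 6.4% |
| Nominal | 90% | 0.4 | 0.566 / 0.501 | 17.7% | 0.354 / 0.301 | 13.5% |
| Shifted | 40% | 1 | 0.606 / 0.601 | 1.6% | 0.398 / 0.394 | 1.1% |
| Shifted | 60% | 1 | 0.609 / 0.601 | 2.6% | 0.407 / 0.399 | 2.2% |
| Shifted | 80% | 1 | 0.616 / 0.602 | 4.5% | 0.415 / 0.401 | 3.8% |
| Shifted | 80% | 0.6 | 0.516 / 0.497 | 5.4% | 0.306 / 0.291 | 4.1% |
| Shifted | 90% | 0.4 | 0.542 / 0.499 | 11.9% | 0.332 / 0.297 | 9.2% |

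Breslow was nearer 1 than Efron in 97-100% of trials, and Efron recovered the assumed hazard ratio within simulation error.

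**4. A different data model.** Simulating potassium trajectories instead (assumed SD 0.40-0.45 between patients and 0.30 within) gave about 6-10% on nominal days and about 4-7% with weekend shifts. An example with shifts: 0.423 v 0.407, so 1 − ln(0.423)/ln(0.407) = 1 − 0.860/0.899 = 4.3%.

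**5. Power (Breslow v Efron).** In the rows above, 10 g loses 0 to 1.4 points (the largest is 80.9% v 82.3%). 5 g loses 0.8 to 5.1 points (90.6% v 91.4%; 90.0% v 95.1%). Over all runs the loss was about 0-2 points for 10 g and about 1-7 points for 5 g.

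**6. No true effect.** With both hazard ratios set to 1, 80% events and scattered visits, Breslow gave 1.006 and 0.991, with rejection rates of 2.7% and 3.0%. There is no inflation.

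**The case against.** Three things can fairly be said against the point.

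*The documents do not choose Breslow.* They choose a procedure and are silent on ties; the default is knowledge about the software. This stands, and it makes the defect one of under-specification. But running the named procedure as written leads to Breslow, and if another method were picked later, that choice could be made after unblinding.

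*The cost is small and uneven.* Test 8 is reached only after tests 1-7 succeed, which selects trials with strong effects. In trajectory simulations with visit shifts, among trials passing proxies for tests 2-7, test 8 lost 0-1.6 points. The overall chance of winning test 9 through the sequence fell by 1.5-5 points. This stands: the loss falls mainly on 5 g.

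*Efron is itself an approximation for events detected at visits.* Interval-censored or discrete-time models are reasonable alternatives. This is true, but it is no argument for leaving the choice unstated.

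A reader might also infer from the schedule that only nine event days are possible. The documents do not support that: SAP 4.2.3.2 counts from actual dates, and protocol Table 2 and SAP Table 2 allow visit windows. The shrinkage computed on nominal days is therefore an upper end.

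**Conclusion.** The point holds as a minor one. Event times will be heavily tied, no ties method is stated, and the default would modestly attenuate the hazard ratio in tests 8 and 9. The log hazard ratio would be about 4-10% smaller with all visits on nominal days and about 2-7% smaller with visits shifted within the window. With few events (40% on placebo) it drops to about 1-2%. Only when most events pile up at the first visits does it reach 9-18%. Power loss is about 0-2 points for 10 g and about 1-7 points for 5 g.

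These sizes rest on assumed event rates, hazard ratios and onset patterns, and on models without the SAP's covariates. The direction does not depend on the scenario.

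A reader might infer that the tests are invalid or could give a false positive. They are not: the bias runs towards no effect, type I error is not inflated, and the primary comparisons (tests 2 and 3) are untouched.

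**What to change.** In SAP 4.2.3.3, under time to hyperkalaemia, add TIES=EFRON (or TIES=EXACT) to the PROC PHREG model, and do so before database lock. This is one model option. It needs no new data and leaves the endpoint, covariates, censoring rule and testing sequence as they are. There is no downside.

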4.2.3.4 Supplementary Analyses of the Secondary Endpoint

One supplementary analysis, aimed at evaluating the impact of disallowed medications use on the likelihood of being normokalemic at the end of RTP, will be performed. The intercurrent event of disallowed medication is again incorporated through a composite endpoint where subjects who receive disallowed medication are classed as "non-responders". The analysis described above will then be replicated using this endpoint.

4.2.3.5 Subgroup Analyses

The secondary efficacy endpoint of the proportion of subjects who remain normokalemic (as defined by S-K between 3.5-5.0 mmol/L, inclusive) at the end of the 28-day randomized treatment study phase will be evaluated in order to explore the consistency of the treatment effect for the following subgroups:

- chronic kidney disease status (yes/no)
- diabetes mellitus status (yes/no)
- heart failure status (yes/no)
- those on RAAS inhibitors (yes/no).

A minimum of 10 responses in total for both arms combined are required for a subgroup analysis to be performed. A single model will be fitted, this model including a treatment by subgroup interaction term in addition to the covariates in the original analysis. Estimates of the treatment effect for each subgroup will be provided, with corresponding confidence intervals. A p-value for the interaction term will also be given.

4.2.3.6 Handling of Dropouts and Missing Data

The S-K levels used for all secondary analyses will be based on the c-lab measurements obtained during the RTP. Missing S-K c-lab values will be replaced as described in Section 3.3.5.

For the number of days subjects remain normokalemic, if an intermediate assessment time point is missing, the time interval will be extended until the next non-missing time point.

4.3 Safety Analyses

The respective safety analysis will be undertaken on the safety analysis sets, separately for the OLP and for the RTP. Safety and tolerability data will be presented by treatment arm and listed, unless otherwise stated.

Safety endpoints will include adverse events (AEs), vital signs (VS), ECGs, clinical laboratory evaluations, and other electrolytes (specifically, serum calcium [S-Ca], serum magnesium [S-Mg], serum sodium [S-Na], serum phosphate [S-PO4], serum bicarbonate [S-HCO3], and blood urea nitrogen [BUN]).

4.3.1 Exposure

4.3.1.1 Definitions and Derivations

Duration of exposure is defined as the number of days between the first and the last dose of IP + 1 day, for each treatment period. Duration of exposure for subjects on every other day dosing is defined as the number of days between the first and the last dose of IP where subjects have a planned dose of IP + 2 days.

Actual Exposure

Actual exposure for each subject will be obtained by summing up the days for which at least one dose of the drug was taken, excluding dose interruptions, and for each treatment arm and overall.

4.3.1.2 Presentation

Individual subject data for study drug administration will be listed for all subjects respectively in the SAF-OLP and SAF-RTP.

Duration of exposure and actual exposure will be summarized for the OLP and the RTP, overall and by treatment group.

4.3.2 Adverse Events

4.3.2.1 Definitions and Derivations

On-treatment adverse events are defined as per Section 3.3.1.2.

The derivations for the following parameters will be the difference between the two dates stated below + 1 day (where first dose date is for either the OLP or RTP first dose date as applicable).

- Time from start of treatment to onset of AE (days)
- Time from last dose to death (days)
- Time from first dose to death (days)
- Time from last dose to onset of AE (days) Calculated for AEs starting after the discontinuation of the study treatment.
- Time from start of treatment to AE becoming serious (days)
- Time from start of treatment to discontinuation of investigational product (due to adverse event) (days).

MedDRA (using the latest or current version) is used to code AEs apart from hypokalemia. The identified risk of hypokalaemia is defined by laboratory values and not by specific MedDRA terms.

Oedema

Oedema related events will be defined by the following MedDRA PT terms: Hypervolaemia Fluid retention, Generalised oedema, Localised oedema, Oedema, Oedema peripheral, Peripheral swelling.

